5.0 STUDY DESIGN AND METHODS

5.1 Study Design

This study is a randomized controlled trial of 70 cancer survivors with clinically significant symptoms of insomnia, randomized to either the STEP-1 intervention group or an enhanced usual care control group. Participants will take part in a single intervention session, during which they will complete baseline measures prior to randomization and then receive their assigned intervention. Participants will complete follow-up measures 4 and 8 weeks post-intervention.

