5.5 Study Measures

Primary outcome measures were previously used with cancer survivors on DFCI 15-336. Measures can be found in Appendix B. Measures are given at all timepoints unless otherwise noted.

The Insomnia Severity Index (ISI)³⁹: The 7-item ISI is the most commonly used measure in insomnia research and has been validated in cancer populations.⁴⁰ It has demonstrated adequate internal consistency, and is sensitive to detect changes in perceived sleep difficulties with treatment.

Profile of Mood States – Short Form (POMS-SF)⁴¹: The Profile of Mood States-Short Form is a commonly used measure of psychological distress that has been validated in cancer populations.⁴² It is a 35-item measure which assesses the mood states of participants, and provides multiple scales including an overall Total Mood Disturbance (TMD) score used here.

PROMIS Sleep Disturbance Short-Form (PROMIS-SD)⁴³: The 8-item PROMIS-SD will be used to assess sleep disturbances and their impact on overall sleep quality. Items include specific sleep problems (e.g., restless sleep) as well as satisfaction with sleep quality and amount of sleep. This measure is given at baseline and 8-week timepoints only.

The Consensus Sleep Diary-Morning (CSD-M)⁴⁴: 9 items from the CSD-M will be used to assess daily sleep quality and sleep latency. Items include time of attempts to fall asleep, number and duration of awakenings, time of final awakening, final rise time, and perceived sleep quality. This measure is given at the 8-week timepoint only.

Physical Health: Physical health will be assessed with one item from the commonly-used SF-12⁴⁵ asking respondents to rate their overall health. Pain will be measured with the commonly used Pain Thermometer⁴⁶ on which participants rate their pain on a scale of 1-10, and a single item asking participants to rate whether they feel “in pain” on a five-point scale.

Sleep Treatment Change: Participants will be asked to report any changes made in sleep behaviors during the study period. This includes changes suggested or recommended in their educational session as well as those not specifically recommended by the study interventions (e.g., new sleep medications, new non-study meditation class). Control condition participants will report on their use of the control resources. This measure is only completed at post-intervention timepoints.

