7.0 STATISTICAL ANALYSIS

Primary Aim: *Evaluate the efficacy of the online STEP-1 intervention to improve insomnia and mood symptoms in cancer survivors.*

This is a randomized 2-arm trial comparing the STEP-1 intervention to an enhanced usual care control condition. Immediately after completing baseline assessment subjects will be randomized (1:1 by the Sealed Envelope platform) to the Experimental group which will receive the STEP-1 intervention, or the Control group which will receive the relaxation based intervention.

Randomization, with block size of 4, will be stratified by age category (40-64 years vs. 65-89 years). Primary endpoint is change in Insomnia Severity Index score from baseline to 8-weeks post-intervention. Secondary endpoint is change in mood symptoms on the Profile of Mood States-Short Form at 8-weeks. Changes in Total Sleep Time and Sleep Efficiency (calculated from the CSD-M), and Total Sleep Disturbance score from the PROMIS-SD will also be evaluated. Data analysis for these variables will follow methods used for our recently completed clinical trial of in-person insomnia interventions delivered to cancer survivors (R03CA201459). Change scores will be treated as continuous variables and primary analyses will compare the arms using 2-way analysis of variance with one between-subjects factor (STEP-1 vs. Control) and one within-subjects factor (time). Cohen's d will be used to quantify within-group effect sizes and Hedges' g adjustment will estimate between-group effect sizes. Primary and secondary endpoints are change at 8 weeks; data collected at 4-week post-assessment timepoints will be analyzed using similar methods.

Sample Size/Power: To meet our aims we require 60 participants with evaluable data, but will enroll 70 as a hedge against attrition. As is common for most CBTI interventions, STEP-1 has demonstrated large effects of $d \geq 1.00$ in our pilot testing). Using this effect size as a reference, the study is conservatively powered to detect an effect size of 0.6 (Primary Aim). With sample size of 60 (30 per arm) the study will have 90% power to detect an effect of this size (two-sided test with $\alpha = .05$). Even in the highly unlikely event that the sample size is reduced to 50 (25 per arm), the study will retain >80% power to detect an effect of this size.

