Missing Data: Participants will be randomized after completing a baseline so complete baseline data are assured. Primary analysis will be an intent-to-treat analysis of randomized subjects. Based on experience using similar data collection methods (Clinical Trials document 2.5), we anticipate minimal missing data (<10%). If needed, we will use multiple imputation to account for missing data. Potential factors in the imputation model include baseline sleep and mood variables. Sensitivity analysis will impute missing change scores with values sampled from an estimated distribution of change scores from the control group participants.

Secondary Aims:

i) Explore participant and program adherence factors associated with clinically significant response to STEP-1. Logistic regression will be used to identify participant demographic and sleep factors (e.g., age, severity of insomnia symptoms) associated with a reduction of ISI scores ≥ 6 points. Variables identified in univariate analysis ($p < .10$) will be entered in a multivariable model estimating STEP-1 response from baseline variables. This analytic approach will also be used to explore how patient adherence factors (e.g., adherence to specific program strategies, number of strategies employed, consistency of adherence) are associated with a reduction of ISI scores ≥ 6 points. Depending on results of these exploratory logistic regression analyses, mediation and moderation analyses can be applied to determine how demographic and sleep variables may themselves be associated with patient adherence factors and clinically significant response to STEP-1 (i.e., reduction of ISI scores ≥ 6 points).

ii) Evaluate feasibility and acceptability of the control intervention. Descriptive statistics will be used to summarize data on duration of the control intervention sessions, as well as sessions missed, interrupted, or rescheduled. Fidelity information from the adherence checklist used to evaluate audiotapes of the control sessions will also be described using descriptive statistics. Scores on the Telehealth Usability Questionnaire, the Credibility/Expectancy Questionnaire, and a study-specific satisfaction checklist will also be summarized. While the focus will be on describing usability and acceptability of the control intervention, comparisons between the control and STEP-1 sessions on these metrics will also be explored using parametric (e.g., t-test) and non-parametric methods (e.g., chi-square, Mann-Whitney).

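### Section 7.0 plans changes in diary-based Total Sleep Time and Sleep Efficiency, but Section 5.5 schedules the diary at week 8 only, so neither change can be computed if that schedule holds.

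*Combined protocol and SAP*

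**What the plan says.** Section 7.0 (Statistical Analysis, Primary Aim) names ISI change as the primary endpoint and POMS-SF change as the secondary endpoint. It then adds three further sleep outcomes: "Changes in Total Sleep Time and Sleep Efficiency (calculated from the CSD-M", together with the PROMIS-SD score. It continues "Change scores will be treated as continuous variables", and specifies a two-way analysis of variance with arm between subjects and time within subjects, Cohen's d within groups and Hedges' g between groups.

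Section 5.5 (Study Measures) sets a default, "Measures are given at all timepoints unless otherwise noted", and then lists exceptions. The PROMIS-SD is given at baseline and week 8. For the Consensus Sleep Diary, "9 items from the CSD-M will be used to assess daily sleep quality and sleep latency", and then: "This measure is given at the 8-week timepoint only".

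On timing, Section 5.1 states: "Participants will take part in a single intervention session, during which they will complete baseline measures prior to randomization". Section 5.2 describes the baseline assessment as covering insomnia and mood, among other measures, and does not name a diary.

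**The concern.** A baseline-to-week-8 change cannot be formed from a measure taken only at week 8. The two sections therefore conflict, and the documents do not show which is in error. If the Section 5.5 schedule is correct, Section 7.0 prescribes an analysis of Total Sleep Time and Sleep Efficiency that cannot be run, and nothing takes its place. Comparing week-8 values, adjusting for some other baseline variable and dropping the outcomes are all possible, and the plan picks none of them. If Section 7.0 is correct, a baseline diary is missing from the schedule. That has to be put right before participants are treated, because a baseline cannot be collected afterwards.

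**Working it through.** **Schedule check.** A change from baseline to week 8 needs the measure at both times. From Section 5.5:

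| Measure | Baseline | Week 4 | Week 8 | Change computable? |
|---|---|---|---|---|
| ISI (primary) | yes | yes | yes | yes |
| POMS-SF (secondary) | yes | yes | yes | yes |
| PROMIS-SD (additional) | yes | no | yes | yes |
| Diary: Total Sleep Time, Sleep Efficiency (additional) | no | no | yes | **no** |

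This affects 2 of 3 additional sleep outcomes and 0 of 2 labelled endpoints. With one timepoint there is no time factor and no within-group d either.

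**Could another part of the plan supply the baseline?** The Missing Data paragraph of Section 7.0 says "Participants will be randomized after completing a baseline so complete baseline data are assured". That can cover only measures scheduled at baseline. Multiple imputation cannot recover a value observed in nobody. The sensitivity analysis reads: "Sensitivity analysis will impute missing change scores with values sampled from an estimated distribution of change scores from the control group participants". For the diary, no control-group change scores would exist to sample from.

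**What a week-8 comparison costs in precision.** Inputs: 30 evaluable participants per arm (Section 7.0, Sample Size/Power); outcome SD set to 1 and equal at both times (assumption); correlation r between baseline and week-8 diary values of 0.3, 0.5 or 0.7 (assumption); correlation ρ between baseline ISI and the week-8 diary value of 0.2, 0.3 or 0.4 (assumption). Half-widths of the 95% confidence interval for the difference between arms, in SD units:

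- Week-8 values, unadjusted: t(0.975, 58) × √(2/30) = 2.002 × 0.2582 = **0.517**.
- Change score: 0.517 × √(2(1 − r)) = **0.612 / 0.517 / 0.400** for r = 0.3 / 0.5 / 0.7.
- Week-8 values adjusted for a baseline diary: t(0.975, 57) × √(2/30) × √(1 − r²) = **0.493 / 0.448 / 0.369**.
- Week-8 values adjusted for baseline ISI and age stratum: t(0.975, 56) × √(2/30) × √(1 − ρ²) = **0.507 / 0.493 / 0.474** for ρ = 0.2 / 0.3 / 0.4.

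Ratio of the unadjusted week-8 interval to the change-score interval: 1/√(2(1 − r)) = 0.85 / 1.00 / 1.29. Ratio to the interval adjusted for a baseline diary: 1/√(1 − r²) = 1.05 / 1.15 / 1.40.

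**The case against.** The strongest case on the other side is that the conflict is real but its consequences are small.

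- **Loose wording.** The word for change might have been meant as a difference between arms. The sentences that follow in Section 7.0 do not allow this: they call for change scores, a time factor and within-group effect sizes.
- **Material not available here.** Section 7.0 says these variables will be analysed by the methods of a recently completed in-person insomnia trial, and the measures are in Appendix B. Neither was available for this review. The earlier trial's methods might settle diary details, but they cannot create a baseline that was not scheduled. Appendix B would have to contradict Section 5.5 to remove the problem.
- **It can still be corrected.** Section 7.0 can be amended at any time before analysis, and it already names the arm comparison and Hedges' g, which carry over to week-8 values. This stands. The analysis is unspecified until the text is corrected; it need not end up being chosen after the data are seen.
- **The Missing Data paragraph is aimed at the primary analysis.** This also stands in part. The paragraph neither causes nor resolves the conflict.
- **Precision may hardly suffer.** This is right for r of 0.5 or less. All the half-widths except 0.517 depend on assumed correlations.

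**Conclusion.** The concern holds. As written, the planned analysis of two additional sleep outcomes cannot be carried out under the stated schedule. This is a contradiction between two intact statements: Section 5.5 makes the diary an express exception to its own default, and distinguishes it from the PROMIS-SD entry directly before it.

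The reach is limited. The labelled endpoints and the PROMIS-SD change are untouched, and randomization still supports an unbiased week-8 comparison. What is lost is the change itself and any within-group description for the diary. There may also be some precision: relative to adjustment for a baseline diary, the unadjusted interval is 5% to 40% wider over assumed r from 0.3 to 0.7. The conclusion is conditional on Section 5.5 being the correct schedule; the precision figures rest on the assumptions listed, the contradiction does not. It should be corrected, but it does not threaten the trial's main result.

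**What to change.** Reconcile Sections 5.5 and 7.0, and say which schedule applies.

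**If the diary is given at week 8 only.** The minimum change is to remove the reference to change for the two diary outcomes. Section 7.0 could read: *Arms will be compared on week-8 Total Sleep Time and week-8 Sleep Efficiency derived from the sleep diary, with Hedges' g; these outcomes are excluded from the change-score, time-factor and within-group analyses. Change in PROMIS-SD is analysed as for the other measures.* State how missing week-8 diary values will be handled, since the control-group change-score imputation cannot apply. Optionally, use a linear model with arm, age stratum (40–64 vs 65–89) and baseline ISI, which recovers a little precision (0.507 to 0.474 SD against 0.517). The cost is wording only, using data already scheduled; the price is that no within-group diary change can be reported.

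**If a baseline diary was intended.** Correct Section 5.5 and give the number of diary days at each timepoint, which is not stated now. A one-day diary adds 9 items and might fit in the existing session. A multi-day diary adds more, and because consent, baseline, randomization and intervention share one session, it would need earlier consent and a collection period before that session. Participants already treated without a baseline diary could not be given one retrospectively.

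### The primary ISI comparison names neither baseline ISI nor the age stratum as a covariate; adding both is a nearly free gain in precision

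*Combined protocol and SAP*

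**What the plan says.** Section 7.0 (Primary Aim) makes 8-week change in ISI the primary endpoint and states: "primary analyses will compare the arms using 2-way analysis of variance with one between-subjects factor (STEP-1 vs. Control) and one within-subjects factor (time"). No other term is listed. On the outcome variable, the plan says: "Change scores will be treated as continuous variables". The same section says that randomization, in blocks of 4, "will be stratified by age category (40-64 years vs. 65-89 years"). It also says "Primary and secondary endpoints are change at 8 weeks; data collected at 4-week post-assessment timepoints will be analyzed using similar methods".

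The section refers to another source: "Data analysis for these variables will follow methods used for our recently completed clinical trial". That trial's methods are not reproduced, so any covariates it used cannot be seen.

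Under Missing Data, the plan notes "Participants will be randomized after completing a baseline so complete baseline data are assured". It gives baseline variables a role only in imputation: "Potential factors in the imputation model include baseline sleep and mood variables". Age and insomnia severity appear again only as candidate predictors in the exploratory responder regression (secondary aim i).

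**The concern.** Baseline ISI and age stratum are known for every participant before randomization, and neither is a stated term in the primary comparison. Subtracting baseline does use it, but fixes its slope at 1 instead of estimating it. When the true slope is well below 1, the change score carries avoidable noise, which matters with only 60 evaluable participants. Leaving out a stratification factor that predicts outcome makes the standard error slightly too large.

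The wording is also unclear. One week-8 change score per person has no time levels, so a within-subjects time factor cannot apply to it. The plan does not say whether time has two levels or three, or which term is the primary test.

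What is at stake is precision. The planned comparison is unbiased and does not inflate type I error.

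**Working it through.** **Inputs from the documents.** Section 7.0: 30 per arm, two-sided α = 0.05, standardized effect 0.6, blocks of 4 within two age strata. The SD on which 0.6 is scaled is not stated.

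**Assumed inputs.** The documents give neither of these:
- r, the correlation of baseline with week-8 ISI: 0.3, 0.5, 0.7.
- k, baseline SD divided by week-8 SD: 0.6, 0.7, 0.8, 1.

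**The plan's own figure.** With time as baseline and week 8, the arm-by-time test is a two-sample t-test on change. Its noncentrality is 0.6 × √(30/2) = 2.32 on 58 df, which gives 62.8% power, against the stated 90%. With 25 per arm it gives 54.7%, against the stated figure of more than 80%. That mismatch is a separate issue; 62.8% is the reference below.

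**Variance.** Set the week-8 SD to 1 and the baseline SD to k.
- Change score: 1 + k² − 2rk.
- Adjusted for baseline: 1 − r².
- Difference: (k − r)². It is never negative, and is zero when r = k, that is, when the slope r/k equals 1.

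Example, r = 0.5 and k = 0.8: change 1 + 0.64 − 0.80 = 0.84; adjusted 0.75; ratio 0.75/0.84 = 0.893.

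**Power.** Noncentral t, 58 df unadjusted and 56 df adjusted. Example with 0.6 in change-score SDs, r = 0.5, k = 1: 2.32/√0.75 = 2.68, which gives 75.1%.

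**CI width.** Mean adjusted width divided by change-score width, simulated: 20,000 runs per cell, n = 60, age-stratified blocks of 4, no age effect.

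Each cell lists r = 0.3 / 0.5 / 0.7.

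| k | Variance ratio | CI-width ratio | Adjusted power, 0.6 in change-score SDs (unadjusted 63%) | Unadjusted power, 0.6 in week-8 SDs (adjusted 67/75/89%) |
|---|---|---|---|---|
| 1 | 0.650/0.750/0.850 | 0.817/0.877/0.932 | 81/75/70% | 49/63/84% |
| 0.8 | 0.784/0.893/0.981 | 0.897/0.955/1.000 | 73/68/64% | 56/70/89% |
| 0.7 | 0.850/0.949/1.000 | 0.933/0.985/1.010 | 70/65/63% | 60/73/89% |
| 0.6 | 0.910/0.987/0.981 | 0.964/1.003/1.001 | 67/63/64% | 63/75/89% |

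The largest gain is at k = 1, r = 0.3: 80.9 − 62.8 = 18.1 points on the change-score scale and 66.8 − 48.9 = 17.9 on the week-8 scale. For k from 0.6 to 0.8 the largest is 73.2 − 62.8 = 10.4 points (66.8 − 56.4 = 10.4 on the week-8 scale). The worst cell is r = k = 0.7, with a CI 1.0% wider and simulated power of 61.5% against 62.3%. The formula ignores chance baseline imbalance, so simulated adjusted power runs about 1 to 2 points below the tabled values.

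**Age stratum.** If age explains a share R² of change-score variance, the unadjusted test has true α = 2·P(t₅₈ > 2.002/√(1 − R²)). This is 4.5% at an assumed R² of 5% and 3.9% at 10%. Simulation (40,000 runs, r = 0.5, k = 0.8) gave 4.5% and 4.1%, against 5.2% and 5.0% for the adjusted model. If age explained up to 10% of residual variance, adjusted power at r = 0.5, k = 1 would go from 75% to 79%.

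**The case against.** A change-score comparison in a randomized trial is standard and valid, so this is a matter of efficiency and not of error. That stands.

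The gain is also not assured. In five of the twelve cells the CI-width ratio is 0.985 or more, and in three it exceeds 1. The largest gains need k = 1, while the entry rule of ISI ≥ 12 (Section 3.1) restricts baseline spread and may push k below 1, where gains are smaller. This too stands, and it is why the k = 0.6 to 0.8 rows matter. It does not reverse the balance: the loss is at most about 1 point of power.

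The computed gain comes from baseline ISI. The age-stratum gain cannot be sized from the documents; the case for including it is mainly that the analysis should match the stratified design.

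The earlier trial's methods might already specify covariates. That is possible, but a reader of this plan cannot tell, and a primary model should be stated where it will be applied.

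Finally, the equivalence with a t-test on change needs time to be baseline and week 8. Readings with three time points were not sized. That is itself a reason to fix the wording.

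**Conclusion.** The point holds as a recommendation to improve precision, not as a correction of an invalid test. Neither covariate is a stated term in the primary comparison, and adding both is favorable or neutral over nearly all of the assumed range. At r = 0.5 the variance falls by 25% (k = 1) or 11% (k = 0.8), equivalent to analyzing about 60/0.750 = 80 or 60/0.893 = 67 participants instead of 60. The size rests on assumed r and k and on the unstated scale of the 0.6 effect, so confidence in the magnitude is moderate. Adjustment does not generally restore the stated 90% power.

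**What to change.** State in Section 7.0 that the primary analysis is a linear model for week-8 ISI with arm, baseline ISI and age stratum (40-64 vs 65-89), reporting the arm coefficient with its 95% CI. With 8-week change as the outcome and the same covariates, the arm coefficient and its standard error are identical. The declared endpoint therefore stays, and the imputed change scores can still be used.

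- Use the same model, with each measure's own baseline, for week-4 ISI, POMS-SF at weeks 4 and 8, and PROMIS-SD at week 8 only (Section 5.5: "This measure is given at baseline and 8-week timepoints only").
- Do not use it for Total Sleep Time and Sleep Efficiency. Section 5.5 schedules the CSD-M only at week 8, so there is no baseline to adjust for.
- Include arm, baseline ISI and age stratum in the imputation model, and name the SD used for Hedges' g.
- Write the model out here and do not rely on the reference to the earlier trial.

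If the ANOVA is kept, add one sentence: time means baseline and week 8, and the arm-by-time term is the primary test.

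The cost is SAP wording and two degrees of freedom, with no new data. The model should be fixed before any outcome data are seen by arm.

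### The power for a between-arm effect of 0.6 is about 63% with 30 per arm and 55% with 25 per arm, not the stated 90% and more than 80%

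*Combined protocol and SAP*

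**What the plan says.** All the relevant statements are in section 7.0 (Statistical Analysis) of the combined protocol and SAP.

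- Endpoint: "Primary endpoint is change in Insomnia Severity Index score from baseline to 8-weeks post-intervention".
- Analysis: "Change scores will be treated as continuous variables and primary analyses will compare the arms using 2-way analysis of variance", with arm as the between-subjects factor and time as the within-subjects factor. Allocation is 1:1.
- Target: "the study is conservatively powered to detect an effect size of 0.6". The reference is the pilot work: "STEP-1 has demonstrated large effects of $d \geq 1.00$ in our pilot testing".
- Power at the planned size: "With sample size of 60 (30 per arm) the study will have 90% power to detect an effect of this size", two-sided at alpha .05.
- Power after heavier loss: for 50 evaluable participants split equally between the arms, the plan's claim is that "the study will retain >80% power to detect an effect of this size".

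The section gives no standard deviation, no correlation between baseline and 8 weeks, no formula and no software. It does not say whether 0.6 is in units of the change-score SD or the raw-score SD. It plans no covariate adjustment for baseline ISI.

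**The concern.** An effect of 0.6 with 30 per arm is a familiar two-sample configuration, and its power is well short of 90%. The two printed figures also look like those for samples twice as large.

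This paragraph is the only justification for requiring 60 evaluable participants and for describing the trial as conservatively powered. If the figures are wrong, the trial has a much larger chance than stated of missing the effect it says it is designed to find. A non-significant result could then be read as good evidence against an effect of 0.6 when it is not. The reassurance about falling to 50 participants would fail as well.

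**Working it through.** **Inputs (all from section 7.0).** Standardised effect d = 0.6; two-sided alpha = .05; 1:1 allocation; n = 30 or 25 per arm; endpoint is change from baseline to 8 weeks.

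**Test.** With two time points, the arm-by-time test in the planned ANOVA is the two-sample t-test on change scores. Because the endpoint is change, d is first read in change-score SD units.

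**Formula.** Power = P(|T| > t crit), where T is noncentral t with 2n − 2 degrees of freedom and noncentrality d × √(n/2).

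**Between-arm power at d = 0.6**

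| n per arm | df | noncentrality | t crit | power | plan says |
|---|---|---|---|---|---|
| 25 | 48 | 0.6 × √12.5 = 2.121 | 2.011 | 54.7% | >80% |
| 30 | 58 | 0.6 × √15 = 2.324 | 2.002 | 62.8% | 90% |
| 35 (all 70 evaluable) | 68 | 0.6 × √17.5 = 2.510 | 1.995 | 69.7% | – |

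The normal approximation gives 64.2% at 30 and 56.4% at 25, so the choice of method does not explain the gap. The shortfall is about 27 points at 30 per arm (90 − 62.8) and at least 25 points at 25 per arm (80 − 54.7).

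**Attempts to reproduce the printed figures**

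| Reading | First figure (plan: 90%) | Second figure (plan: >80%) | Fits the text? |
|---|---|---|---|
| Two-sample, one-sided | 74.3% | 67.2% | No; the plan is two-sided |
| 60 and 50 entered as per-arm sizes | 90.3% | 84.4% | No; they are totals |
| Paired test within one arm, n = 30 and 25 | 88.8% | 82.1% | No; it does not compare arms |
| Raw-SD units, change score, correlation 0.75 | 89.8% | 83.6% | Correlation and scaling not stated |
| Raw-SD units, baseline-adjusted, correlation 0.70 | 89.2% | 82.9% | Not stated; adjustment not planned |

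**Correlation needed.** If 0.6 is in raw-SD units and ρ is the baseline to 8-week correlation, the effect on the change-score scale is 0.6/√(2(1 − ρ)). At 30 per arm, 90% power needs an effect of 0.851. Solving, ρ = 1 − (0.6/0.851)²/2 ≈ 0.75. For a baseline-adjusted analysis the effect is 0.6/√(1 − ρ²), so ρ = √(1 − (0.6/0.851)²) ≈ 0.71.

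Over an assumed range of ρ, change-score power at 30 per arm in raw-SD units is:

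| ρ (assumed) | 0.3 | 0.5 | 0.6 | 0.7 | 0.75 | 0.8 |
|---|---|---|---|---|---|---|
| Power | 48.9% | 62.8% | 72.4% | 83.9% | 89.8% | 95.1% |

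**What the design can detect.** At 30 per arm: d = 0.74 with 80% power and 0.85 with 90%. At 25 per arm: d = 0.81 with 80%. Detecting 0.6 needs 45 per arm (90 in total) for 80% power, or 60 per arm (120 in total) for 90%.

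**The case against.** The strongest reply is that the plan never defines the standardiser. If 0.6 is in raw ISI SD units, one correlation of about 0.75 reproduces both printed figures, so a coherent between-arm calculation could lie behind them. That is arithmetically right. But no section states a correlation or that scaling, the endpoint is change, and baseline adjustment is not the planned analysis. Power that depends on an undeclared and fairly high correlation is not supported by the plan as written.

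A second reply is that the pilot effect was 1.00 or more. If the true between-arm effect were 1.00, power would be about 97% at 30 per arm and 93% at 25. However, the plan does not say whether the pilot figure is within-group or between-arm. The comparator here is a relaxation session that section 5.4 describes as controlling for attention and non-specific factors. The power sentences in any case concern 0.6.

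Two further points stand. The origin of the error cannot be established: totals used as per-arm sizes, a within-arm test and an undeclared correlation all come close to the printed figures. And a wrong power statement does not bias the estimate or inflate type I error. The planned between-group Hedges' g would also help a reader interpret a null result.

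**Conclusion.** The concern holds. For the between-arm comparison of 8-week ISI change, with 0.6 in change-score SD units, the type II error is about 37% rather than 10% at 30 per arm, and about 45% rather than under 20% at 25 per arm. The same values result if 0.6 is in raw-SD units and the correlation is 0.5. They would be overturned only by a correlation of about 0.75 on the raw scale, or 0.71 with an adjustment the plan does not specify. The conclusion does not depend on how the error arose. Since this is the sole justification for the sample size on the primary endpoint, it must be corrected.

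**What to change.** First establish which test, standardiser and correlation produced the printed figures. If a raw-SD scale and a correlation were used, write both into section 7.0 and give evidence for the correlation.

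Otherwise replace the power statement with, for example: *For a between-arm difference in 8-week ISI change, two-sided alpha .05, 30 evaluable participants per arm give 63% power for d = 0.6, 80% power for d = 0.74 and 90% power for d = 0.85; 25 per arm give 55% power for d = 0.6 and 80% power for d = 0.81.* Remove the description of the trial as conservatively powered for 0.6.

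This costs wording only. Enrolment stays at 70, and the stated power becomes less favourable.

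If the sponsor wants credit for baseline adjustment, the primary analysis must be changed to a baseline-adjusted model and the assumed correlation stated. That is more than a wording change. With 0.6 in change-score SD units the effective size becomes 0.6 × √(2/(1 + ρ)). At 30 per arm this gives 0.671 and 72% power for ρ = 0.6, rising to 0.744 and 81% for ρ = 0.3, still below 90%.
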